9.6.4 Vital Signs

Depending on the size and scope of changes, summaries of vital signs data (blood pressure (BP), respiratory rate, heart rate and temperature) over time and/or changes from baseline overtime may be provided. Shifts in vital sign values from baseline over time may also be tabulated if required.

9.6.5 Physical Measurements

The analysis of body weight may include summary statistics at selected time points for each treatment cohort.

9.6.6 Electrocardiogram

Summaries over time and/or changes from baseline over time will be provided for all ECG parameters. Subjects' maximum change from baseline in (QTcF, QTcB) will be categorized and the number and percentage of subjects in each cohort will be summarized. Subjects' maximum post baseline values will also be categorized and the number and percentage of subjects in each group will be summarized.

Subjects will be categorized into the following groups per their maximum change from baseline in QTcF and QTcB. Unscheduled assessments will be included in the determination of the maximum change.

- ≤ 30 msec
- $>30 - 60$ msec
- >60 msec

The number and percentage of subjects in each group will be summarized.

Subjects will also be categorized into the following groups per their maximum post baseline QTcF. Unscheduled assessments will be included in the determination of the maximum post baseline value.

- ≤ 450 msec
- $>450 - 480$ msec
- $>480 - 500$ msec
- >500 msec

The number of subjects in each group will be summarized for each cohort.

9.6.7 Antibody Formation

A listing of subjects who develop anti-AMG 404 antibodies (binding) may be provided. Blood sample(s) for antibody testing are to be collected according to the time points specified in the Schedule of Activities for the measurement of anti-AMG 404 antibodies. Samples testing positive for binding antibodies may be further characterized. Additional blood samples may be obtained to rule out anti-AMG 404 antibodies during the study. Subjects who test positive for anti-AMG 404 antibodies at the final scheduled antibody timepoint and have clinical sequelae that are considered potentially related to the anti-AMG 404 antibody response will be asked to return for additional follow-up testing. Sample collection and testing will occur approximately every 3 months from the safety follow up visit until: (1) anti-AMG 404 antibodies are no longer detectable; or (2) the subject has been followed for a period of at least 1-year (± 4 weeks) post administration

of AMG 404. All follow-up results, both positive and negative, will be communicated to the sites. More frequent testing (eg, every month) or testing for a longer period of time may be requested in the event of safety-related concerns.

The incidence and percentage of subjects who develop anti-AMG 404 antibodies, will be tabulated overall, and by cohort.

9.6.8 Exposure to Investigational Product

Descriptive statistics will be produced to describe the exposure to investigational product by treatment dose. Number of cycles started, Number of doses of investigational product, the cumulative dose by unit and average dose delivered per day and duration of exposure will be summarized.

Summaries of the number and percentage of subjects with dose change/withheld and reason for change/withheld will be provided. Details for each AMG 404 administration will be listed for every subject. In addition, a listing of the unique manufacturing lot numbers, and a listing of the subjects administered each manufacturing lot number will be provided.

9.6.9 Exposure to Other Protocol-specified Treatment

[figure not shown]
Not applicable.

9.6.10 Exposure to Concomitant Medication

All medication will be coded using the WHO drug dictionary.

The number and proportion of subjects receiving concomitant medications will be summarized by preferred term or category.

9.7 Other Analyses

9.7.1 Analyses of Pharmacokinetic or Pharmacokinetic/Pharmacodynamic Endpoints

The PK parameters of AMG 404 including, but not limited to, C_{max} , t_{max} , and AUC for serum AMG 404 will be estimated using non-compartmental methods for subjects where intense PK sampling was collected (ie, subjects in Cohorts 1-6 [REDACTED], at least 10 subjects in Cohorts 7-9). [REDACTED]

[REDACTED] The parameter estimates will be summarized by dose level using means, geometric means, standard deviations, coefficients of variation, medians, minimums, and maximums. Individual concentration-time profiles will be summarized by dose level. [REDACTED]

[REDACTED]. Summary statistics will be computed for each sampling time and parameter as appropriate. The relationship between AMG 404 exposure and efficacy/safety may be conducted.

Nominal sampling times will be used for individual concentration-time plots and tables. Actual dose administered and actual sampling times will be used for the calculation of PK parameters for each subject. The reasons for excluding any sample from the analyses will be provided. Above analyses will be conducted by Amgen Clinical Pharmacology Modeling and Simulation (CPMS).

The relationship between AMG 404 exposure and QT/QTc interval changes may be inspected graphically and model-based PK/pharmacodynamic analyses may be conducted to examine the relationship further.

[REDACTED]

11. Literature Citations / References

AMG 404 Investigator's Brochure. Thousand Oaks, CA. Amgen Inc.

Brookmeyer, R. and Crowley, J. (1982) A Confidence Interval for the Median Survival Time, *Biometrics*, 38, 29 - 41.

Kalbfleisch, J.D. and Prentice, R.L. (1980) *The statistical analysis of failure time data*. John Wiley and Sons, New York.

M. Hidalgo et al. (eds.), *Principles of Anticancer Drug Development*, Cancer Drug Discovery and Development, DOI 10.1007/978-1-4419-7358-0_2.

[figure not shown]
12. Prioritization of Analyses

There is no prioritization of analyses.

13. Data Not Covered by This Plan

Not applicable.

14. Appendices

[figure not shown]

Appendix B. Code Fragments

Example:

95% Confidence Interval by Clopper Pearson Method:

```
proc freq data=<data> ;  
tables <variable>*<variable> / binomial(exact) ;  
run;
```

- **Code fragment for K-M method:**

```
proc lifetest data=data1 method=km conftype=loflog alphaqt=0.05  
by cohortn;  
time avail*cnsr (1);  
run;
```

Appendix C. BOR per RECIST (v1.1) Criteria

The protocol requires that a PD must be confirmed. The analysis of modified RECIST 1.1 BOR endpoints will follow standard RECIST 1.1 convention which does not require confirmation of PD.

Best Overall Response (BOR) determination per RECIST 1.1 is given in below in [Table 14-2](#), the BOR considered is a Confirmed BOR.

Table 14-2. BOR per RECIST 1.1

Criterion	Time point T1 Response	T1 ≥ 49 days after C1D1?	Time point T2 Response	T2 ≥ 49 days after C1D1?	T2 ≥ 28 days after T1?	BOR	
C1	CR	Yes	CR	-	Yes	CR	
C2			CR	-	No	SD	
C3		No	-	PR, SD	-	-	Query data*
C4				PD	-	-	SD
C5				NE, No further evaluations			SD
C6				CR	-	Yes	CR
C7				CR	Yes	No	SD
C8				PR, SD	-	-	Query data*
C9		PD	-	-	PD		
C10		NE, No further evaluations			NE		
C11	PR	Yes	CR, PR	-	Yes	PR	
C12			CR, PR	-	No	SD	
C13		No	-	SD	-	-	SD
C14				PD	-	-	SD
C15				NE, No further evaluations			SD
C16				CR, PR	-	Yes	PR
C17				CR, PR	Yes	No	SD
C18				SD	Yes	-	SD
C19		PD	-	-	PD		
C20		NE, No further evaluations			NE		
C21	SD	Yes	CR, PR, SD, PD, NE, no more evaluation			SD	
C22			CR, PR, SD	Yes	-	SD	
C23		No	-	CR, PR, SD	No	-	NE
C24				PD	-	-	PD
C25				NE, No further Evaluations			NE
C26	PD	-	-	-	-	PD	
C27	NE	-	NE, No further evaluations			NE	
C28		-	CR, PR, SD	Yes	-	SD	
C29		-	CR, PR, SD	No	-	NE	
C30		-	PD	-	-	PD	

CR = complete response, PR = partial response, SD = stable disease, PD = progressive disease, and NE = not evaluable.

*If a CR is truly met at first time point, then any disease seen at a subsequent time point, even disease meeting PR criteria relative to baseline, makes the disease PD at that point (since disease must have reappeared after CR). Best response would depend on whether minimum duration for SD was met. However, sometimes 'CR' may be claimed when subsequent scans suggest small lesions were likely still present and in fact the patient had PR, not CR at the first time point. Under these circumstances, the original CR should be changed to PR and the best response is PR.

A CR must be confirmed by CR, a PR can be confirmed by a PR or CR.

An unlimited number of intermittent assessments of NE can occur between the initial response and the confirmation. For example, BL, CR, NE, NE, NE, CR – the CR at post baseline 1 is confirmed at post baseline 5.

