#### 10.2.2 Efficacy Assessments

Tumor evaluations (by CT or MRI as appropriate) and tumor markers, if applicable, are to be collected at time points specified in the Schedule of Activities (Section 3.2). Imaging may also be performed more frequently if clinically necessitated at the discretion of the managing physician. Radiographic response (Complete Response, Partial Response) requires confirmation by a repeat, consecutive scan at least 4 weeks after the first documentation of response and may be delayed until the next scheduled scan to avoid unnecessary procedures. Radiographic progression (Progressive Disease) requires confirmation by a repeat, consecutive assessment 4-6 weeks after the first detection of radiological progression. Upon discussion with the Sponsor, in the absence of clinical deterioration and with the subject's consent (subject must sign addendum consent), subjects may continue to receive AMG 404 treatment after confirmation of radiographic progressive disease as long as they continue to derive clinical benefit, until clinical disease progression, or intolerance of study treatment, or clinically significant deterioration of health status requiring discontinuation, or the subject withdrawal of consent, whichever occurs first [REDACTED]

[REDACTED]). In some circumstances it may be difficult to distinguish residual disease from scar or normal tissue. When the evaluation of CR depends on this determination, the residual lesion may be further investigated by additional scans to be discussed with Sponsor, or possibly fine needle aspirate/biopsy, to confirm the CR status. Subjects who continue on AMG 404 treatment, and/or other cancer therapies following confirmation of radiographic progressive disease will have radiological imaging assessment every 8 ( $\pm$  1) weeks thereafter **following the confirmation of radiological progression** for Cohorts 1-9, [REDACTED]

If a subject discontinues treatment for reasons other than progression, tumor evaluations should continue according to the Schedule of Activities (Section 3.2) until progression or start of a new treatment regimen.

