### 13.10 Appendix 10. Modified Response Evaluation Criteria in Solid Tumors Version 1.1 (Modified RECIST 1.1)

This study utilizes modified RECIST 1.1 criteria, which includes required confirmation of disease progression, and the following modification to RECIST 1.1:

- Up to 5 target lesions per organ and 10 total are allowed (compared to 2 per organ and 5 total for standard RECIST 1.1) to increase lesion sampling and reduce assessment error.

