**Overall Response: Confirmation of Complete Response (CR) and Partial Response (PR) required**

Overall Response First Time Point	Overall Response Second Time Point	Best Overall Response
CR	CR	CR
CR	PR	SD, PD or PR †
CR	SD	SD provided minimum criteria for SD duration met, otherwise, PD
CR	PD	SD provided minimum criteria for SD duration met, otherwise, PD
CR	NE	SD provided minimum criteria for SD duration met, otherwise, NE
PR	CR	PR
PR	PR	PR
PR	SD	SD
PR	PD	SD provided minimum criteria for SD duration met, otherwise, PD
PR	NE	SD provided minimum criteria for SD duration met, otherwise, NE
NE	NE	NE

† If a CR is truly met at first time point, then any disease at a subsequent time point, even disease meeting PR criteria relative to baseline, makes the disease PD at that point (since disease must have reappeared after CR). Best response would depend on whether minimum duration for SD was met. However, sometimes “CR” may be claimed when subsequent scans suggest small lesions were likely still present and in fact the subject had PR, not CR at the first time point. Under these circumstances, the original CR should be changed to PR and the best response is PR.

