#### **Confirmation Measurement / Duration of Response**

- **Response Confirmation** - In non-randomized trials where response is the primary endpoint, confirmation of PR and CR is required to ensure responses identified are not the result of measurement error.
- **Duration of overall response** – The duration of overall response is measured from the time measurement criteria are first met for CR/PR (whichever is first recorded) until the first date the recurrent or progressive disease is objectively documented.
- **Duration of Stable Disease** - SD is measured from the start of the treatment until the criteria for disease progression are met, taking as reference the smallest measurements recorded since the treatment started.

## Amendment 6

**Protocol Title: A Phase 1 Study to Evaluate Safety, Tolerability, Pharmacokinetics and Pharmacodynamics of AMG 404, a Programmed Death-1 (PD-1) Antibody, [REDACTED] in Patients With Advanced Solid Tumors**

Amgen Protocol Number AMG 404 20180143

EudraCT Number: 2018-004268-80

NCT Number: NCT3853109

Amendment Date: 20 May 2022

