2.1 Objectives and Endpoints

Objectives	Endpoints
Primary	

To evaluate the safety and tolerability and determine the recommended phase 2 dose (RP2D) of AMG 404 in patients with advanced solid tumors	
Dose limiting toxicities (DLTs), treatment-emergent adverse events, treatment-related adverse events, and changes in vital signs, and clinical laboratory tests
Secondary	

To evaluate the pharmacokinetics (PK) of AMG 404, as a monotherapy [REDACTED]	
PK parameters of AMG 404 including, but not limited to, maximum observed serum concentration (C_{max}), time to achieve C_{max} (t_{max}), and area under the serum concentration-time curve (AUC)

To assess the immunogenicity of AMG 404, as a monotherapy [REDACTED]	
Subject incidence of anti-AMG 404 antibodies

To evaluate the preliminary antitumor activity of AMG 404, as a monotherapy [REDACTED]	
Objective tumor response, duration of overall response, progression-free survival, disease control rate (DCR), and duration of stable disease measured by CT/MRI and assessed per modified RECIST 1.1

Exploratory

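### The SAP lets a response after progression count towards best overall response, unlike the protocol, and its endpoint table still names a confirmed-PD criterion that its own definitions drop

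*SAP*

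**What the plan says.** **Window for BOR.** SAP Section 5 (Best Overall Response) uses every post-baseline assessment made before the next anticancer therapy starts, and takes the best response observed in the order CR, PR, SD, PD, NE. It sends the reader to Appendix C, Table 14-2, for the algorithm. Protocol Section 13.10 (Evaluation of Overall Response) counts responses only up to the end of treatment or progression/recurrence. Protocol Section 10.2.2 foresees scans after PD: "subjects may continue to receive AMG 404 treatment after confirmation of radiographic progressive disease as long as they continue to derive clinical benefit", with imaging about every 8 weeks.

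**PD rule.** The endpoint tables (Protocol Synopsis and Section 5.1; SAP Section 2.1) have objective response, duration of response (DOR), PFS, disease control rate (DCR) and duration of stable disease (DoSD) "measured by CT/MRI and assessed per modified RECIST 1.1". Protocol Section 13.10 explains the label: "This study utilizes modified RECIST 1.1 criteria, which includes required confirmation of disease progression". It also raises the target-lesion limit to 5 per organ and 10 in total. Protocol Section 10.2.2 adds: "Radiographic progression (Progressive Disease) requires confirmation by a repeat, consecutive assessment 4-6 weeks after the first detection of radiological progression". SAP Appendix C then states: "The analysis of modified RECIST 1.1 BOR endpoints will follow standard RECIST 1.1 convention which does not require confirmation of PD". SAP Section 5 names plain RECIST 1.1 for BOR, DCR, objective response and PFS, and defines PFS by the first documentation of radiological progression. DOR and DoSD also end at first documentation of progression. They name no RECIST version and take only their censoring from PFS.

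**The concern.** Protocol and SAP end the BOR window at different points, and the difference falls where this trial expects data, because treatment and imaging may continue past PD. Followed literally, the SAP text can turn a subject who progressed and later responded into a responder, while the protocol text would not. In a single-arm, open-label study, that choice should not be left to programming.

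The second problem is a label that no longer matches the definitions beneath it. A reader of SAP Section 2.1 would expect confirmed PD for all five tumor endpoints. A reader of Section 5 and Appendix C would derive BOR and PFS with unconfirmed PD, and would have to infer the rule for DOR and DoSD.

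**Working it through.** **1. Window.** Take scans SD d56, PD d112, PD d140, PR d196, PR d252, with the subject still on treatment and no new therapy. The rows used are from SAP Table 14-2. The SAP does not say how scan pairs combine. I assume each successive pair is read and the best result kept. Some such sweep seems needed: row C21 returns SD when the first scan is SD on or after day 49, so using the first pair alone, SD, PR, PR could never be PR.

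| Pair | Check | Row | Result |
|---|---|---|---|
| SD d56, PD d112 | 56 ≥ 49 | C21 | SD |
| PD d112, PD d140 | first is PD | C26 | PD |
| PD d140, PR d196 | first is PD | C26 | PD |
| PR d196, PR d252 | 252 − 196 = 56 ≥ 28 | C11 | PR |
| PR d252, none | 252 ≥ 49 | C15 | SD |

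- SAP window (no stop at PD): best = **PR**.
- Protocol window, unconfirmed PD: stops at d112, best = **SD**.
- Protocol window, confirmed PD: 140 − 112 = 28 days = 4 weeks, within the 4-6 weeks required, so PD is confirmed and best = **SD**.

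The windows therefore disagree whichever PD rule is used. ORR changes. DCR does not in this example, because SD and PR both count as control in SAP Section 5.

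**2. PD rule.** Now take SD d56, PD d112, PR d140, PR d196. The SAP window gives PR. The protocol window gives SD if it stops at first PD, and PR if PD must be confirmed, because the d140 scan does not confirm it. PFS has an event at d112 under unconfirmed PD and none in these data under confirmed PD.

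The SAP texts side by side:

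| Endpoint | Section 2.1 | Section 5 / Appendix C |
|---|---|---|
| Objective response, DCR (through BOR) | modified RECIST 1.1 | plain RECIST 1.1; PD unconfirmed for BOR |
| PFS | modified RECIST 1.1 | first documentation, RECIST v1.1 |
| DOR, DoSD | modified RECIST 1.1 | first documentation; no version or confirmation rule |

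**3. Size per subject.** The shift is 1/n: 1/40 = 2.5, 1/20 = 5.0 and 1/12 = 8.3 points. Exact 80% limits are the 0.10 quantile of Beta(x, n−x+1) and the 0.90 quantile of Beta(x+1, n−x). The plan's own intervals at its 25% planning rate (Protocol Section 11.1, SAP Section 3.2) reproduce:

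| n | Plan states | Recomputed at 25% | One more responder |
|---|---|---|---|
| 40 | 16% to 36% | 10/40: 16.2% to 35.9% | 11/40 = 27.5% (18.3% to 38.5%) |
| 20 | 13% to 42% | 5/20: 12.7% to 41.5% | 6/20 = 30.0% (16.6% to 46.7%) |
| 12 | 10% to 48% | 3/12: 9.6% to 47.5% | 4/12 = 33.3% (15.4% to 55.9%) |

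**The case against.** **Table 14-2 may already stop at PD.** Row C26 gives BOR = PD when the first scan is PD, whatever follows, and Section 5 defers to that table. A reader might infer that PD, PR, PR is counted as a response under the SAP. The documents do not establish that, since C26 can be read as final for PD at the first scan. It does not settle PD after a non-PD scan, and nothing visible does. The example above is therefore of that kind.

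**PFS has a rule.** A reader might infer that the SAP leaves PFS open between confirmed and unconfirmed PD, and size this by a week-8 PD with no later scan being an event under one rule and censored under the other. Section 5 does not support that: first documentation under RECIST v1.1 is a rule, and most naturally the unconfirmed one. What stands is its conflict with the Section 2.1 label.

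**DOR and DoSD lean the same way.** Both run to first documentation. The protocol's response table is headed "Overall Response: Confirmation of Complete Response (CR) and Partial Response (PR) required", with no mention of PD. DOR there runs "until the first date the recurrent or progressive disease is objectively documented", and "SD is measured from the start of the treatment until the criteria for disease progression are met". This points to unconfirmed PD, so one explicit sentence is all that is missing.

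**'Modified' means more than confirmed PD.** It also covers the lesion count, and Appendix C keeps the word while dropping confirmation. Replacing the label with plain RECIST 1.1 could remove the lesion-count change by accident. This objection stands and shapes the fix.

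**Post-PD scans.** A reader of Table 3-1, footnote 5 might infer that scans after stopping are scheduled only for subjects who stop for reasons other than progression. Protocol Section 10.2.2 also schedules imaging for those who go on to AMG 404 and/or other cancer therapy after confirmed PD.

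**Redaction.** Parts of the SAP appendices are not shown, so silence is claimed only for the visible text.

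**Conclusion.** Two points hold. First, the SAP's BOR window lacks the protocol's stop at progression and at end of treatment, so a response after PD that followed a non-PD scan can count in ORR under the SAP and not under the protocol. The example depends on reading Table 14-2 over successive pairs. Second, the modified RECIST 1.1 label in SAP Section 2.1 conflicts with Appendix C for BOR and with Section 5 for PFS, while DOR and DoSD imply unconfirmed PD without saying so.

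The size is known only per subject. The documents give no rate of response after PD or of unconfirmed PD, so no total effect can be stated. At n=40 one subject's shift is small beside an 80% interval of roughly 20 points (16.2% to 35.9%); at n=12 it is 8.3 points. A reader might infer that the trial's main conclusions are at risk. They are not: these endpoints are secondary and descriptive, and the primary endpoints are safety. The change is still worth making before the analysis is programmed.

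**What to change.** - **BOR window.** In SAP Section 5 and Table 14-2, end it at the earlier of first documented PD and the start of subsequent anticancer therapy. Decide whether end of treatment also closes it, and make SAP and Protocol Section 13.10 agree. State how scan pairs in Table 14-2 combine.
- **PD rule.** State once in SAP Section 5 that the Appendix C rule (PD dated at first documentation, no confirmation needed) applies to BOR, ORR, DCR, PFS, DOR and DoSD.
- **Label.** Keep 'modified' in SAP Section 2.1, with a note that for analysis it retains the limit of 5 target lesions per organ and 10 in total, but not PD confirmation.
- **Wording only.** Delete the stray 'or progression' from the CR/PR confirmation sentence in SAP Section 5. Replace 'partial or complete control' with CR, PR or SD in the Protocol Synopsis, Protocol Section 11.4.2.2 and SAP Section 9.5.2, to match the DCR definition in SAP Section 5.

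The cost is a few sentences, mostly in the SAP. A confirmed-PD sensitivity analysis is optional. It would need a second set of derivations and a rule for PD with no later scan.

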BOR for a subject is the best observed disease response per RECIST 1.1 in the following order: CR, PR, SD, PD, or NE. A best overall response of CR and PR require confirmation by a repeat, consecutive scan at least 4 weeks after the first documentation of response or progression.

A best overall response of SD requires an on-study imaging of SD or better no earlier than 7 weeks (49 days) after cycle 1 day 1.

Please refer [Appendix C](#) for deriving BOR algorithm as per RECIST 1.1.

Change from Baseline

Change from Baseline is the arithmetic difference between post-dose assessments and Baseline value.

Change (absolute) from Baseline = (Post-baseline Value – Baseline Value)

Change (percent) from Baseline = [(Post-baseline Value – Baseline Value)/Baseline Value] x 100

C_{max}

The maximum concentration of drug obtained in the serum.

Disease control rate

DCR is defined as the proportion of subjects in whom objective response (CR or PR) or stable disease (SD) is determined as per RECIST v1.1.

Dose Limiting Toxicity (DLT)

Defined as the severe toxicities during the first cycle of cancer therapy. A Dose Limiting Toxicity (DLT) is defined as any AE (meeting the criteria listed in section 8.4.2 of protocol) occurring during the first treatment cycle of AMG 404 (day 1 through day 28) where relationship to AMG 404 cannot be ruled out.

The DLT window (ie, DLT-evaluable period) will be the first 28 days of AMG 404 treatment (starting cycle 1, day 1).

Duration of Overall Response (DOR)

Duration of overall response is defined as the time from the first documentation of objective response, until the first documentation of disease progression, or death due to any cause, whichever occurs first. Only subjects who have achieved objective response will be evaluated for DOR. Duration of response will be censored as per PFS censoring rule.

Duration of Stable Disease (DoSD)

Duration of stable disease will be measured from the start of treatment until the first documentation of disease progression or death due to any cause. DoSD will be calculated only in subjects with best overall response SD.

Duration of stable disease will be censored as per PFS censoring rule.

End of treatment

Defined as the last assessment for the protocol specified treatment phase of the study for an individual subject.

End of Study

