9.5.2 Analyses of Secondary Efficacy Endpoint(s)

For all subjects treated at the RP2D and separately by cohort, the following analyses will be done. The proportion of subjects with confirmed objective tumor response (partial and complete response) and disease control rate (DCR) (partial or complete control) with corresponding exact 80% CI will be calculated and tabulated. Similarly, the proportion of subjects and 80% CI will be tabulated for 1-year duration of overall response, 1-year PFS, 1-year duration of stable disease and 1-year OS. Kaplan-Meier curve will be presented for duration of overall response, PFS, OS and duration of stable disease with estimates for rate and 80% CI at selected weeks based on the Brookmeyer and Crowley method ([Brookmeyer & Crowley, 1982](#)) if data allows.

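### SAP Table 14-2 footnote: a CR re-labelled as PR is given best response PR with no confirmation condition, and the SAP extends this to CR followed by SD

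*SAP*

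**What the plan says.** SAP Appendix C derives best overall response (BOR) in Table 14-2 and states that "the BOR considered is a Confirmed BOR". Rows C3 (first CR on or after day 49) and C8 (first CR before day 49) cover a second time point of PR or SD. Both return an instruction to query the data, with a dash in the column for T2 on or after day 49 and in the column for T2 at least 28 days after T1.

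The footnote on that instruction has two branches. If the CR was real, later disease counts as PD and BOR depends on the minimum SD duration. The second branch applies where "sometimes 'CR' may be claimed when subsequent scans suggest small lesions were likely still present and in fact the patient had PR". For that branch it says: "Under these circumstances, the original CR should be changed to PR and the best response is PR".

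Other text in the plan requires confirmation:

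- A line in the notes below the footnote says: "A CR must be confirmed by CR, a PR can be confirmed by a PR or CR".
- SAP Section 5, under Best Overall Response, says: "A best overall response of CR and PR require confirmation by a repeat, consecutive scan at least 4 weeks after the first documentation".
- SAP 9.5.2 tabulates "The proportion of subjects with confirmed objective tumor response (partial and complete response", with an exact 80% CI.

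The confirmation table in Protocol Appendix 10 carries the same footnote sentence but attaches it only to CR followed by PR. CR followed by SD has its own row: "SD provided minimum criteria for SD duration met, otherwise, PD".

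**The concern.** A query is not a BOR category, and the footnote is the only text that turns it into one. Once the CR is re-labelled, the footnote's result is PR whatever T2 was and however soon it followed. The same two scans entered as PR from the start would be SD in several of these cases. BOR would then depend on how the first scan was first labelled and not on the corrected data.

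At stake is whether a response that no later scan confirms can be counted in a rate described as confirmed. Such a subject would also enter the duration-of-response analysis (responders only) and leave the duration-of-stable-disease analysis (BOR of SD only). For CR followed by SD, the SAP also departs from the protocol it implements.

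**Working it through.** **Row logic.** Take a CR at T1 that has been re-labelled PR. Compare the footnote read literally with the result when the corrected PR is passed through the table's own PR rows.

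| T2 | Timing | Footnote, literal | Via C11-C18 |
|---|---|---|---|
| PR | at least 28 days after T1 | PR | PR (C11, C16) |
| PR | under 28 days; T1 on or after day 49 | PR | SD (C12) |
| PR | under 28 days; T1 before, T2 on or after day 49 | PR | SD (C17) |
| SD | T1 on or after day 49 | PR | SD (C13) |
| SD | T1 before, T2 on or after day 49 | PR | SD (C18) |
| SD, or PR under 28 days | both before day 49 | PR | no row |

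The two routes agree only in the first line, which is a properly confirmed PR. For T2 = SD, the protocol table gives SD or PD and never PR.

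**How often it can arise.** Scans are every 8 (±1) weeks (Protocol Table 3-1, footnote 5).

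- Even with the windows used in opposite directions (week 9, then week 15), scheduled scans are 6 weeks = 42 days apart. The earliest scheduled scan is at 7 weeks = 49 days. So T2 within 28 days of T1, or T1 before day 49, needs an unscheduled scan.
- CR followed by SD can occur on schedule, but the response definitions leave little room. Let B be the baseline sum and s the re-read sum at T1, taken as the nadir. SD at T2 needs a sum above 0.7B (not PR) and not both 20% and 5 mm above s (not PD). For s up to 25 mm the 5 mm limit binds, since 20% of 25 mm is 5 mm. Hence 0.7B < s + 5, or B < (s + 5)/0.7.
- With s = 5 mm, B < 10/0.7 = 14.3 mm.
- For a single nodal target re-read at 10 mm (CR requires under 10 mm), B < 15/0.7 = 21.4 mm. Nodes are measurable from 15 mm, so this case is possible.

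**Size.** Exact (Clopper-Pearson) 80% limits for x of n are: lower = the 0.10 quantile of Beta(x, n-x+1); upper = the 0.90 quantile of Beta(x+1, n-x).

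The plan's own figures (Protocol 11.1, SAP 3.2) at 25% ORR reproduce, up to rounding:

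- 10/40: 16.2-35.9% (stated 16-36%).
- 5/20: 12.7-41.5% (stated 13-42%).
- 3/12: 9.6-47.5% (stated 10-48%).

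If one of those responders is instead scored SD:

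| n | With the subject as PR | With the subject as SD | Change in ORR |
|---|---|---|---|
| 40 | 10/40 = 25.0% (16.2-35.9%) | 9/40 = 22.5% (14.1-33.2%) | 1/40 = 2.5 points |
| 20 | 5/20 = 25.0% (12.7-41.5%) | 4/20 = 20.0% (9.0-36.1%) | 1/20 = 5.0 points |
| 12 | 3/12 = 25.0% (9.6-47.5%) | 2/12 = 16.7% (4.5-38.5%) | 1/12 = 8.3 points |

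The responder counts are illustrative. The number of affected subjects is an assumption.

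**The case against.** The strongest reply is that Table 14-2 does not score these cases as PR. It asks for a query, and PR follows only if the query shows that the first scan was a PR. The confirmation line in the table notes, the statement that the BOR is confirmed, SAP Section 5, SAP 9.5.2 and Protocol 10.2.2 all require confirmation. A programmer could therefore reasonably pass the corrected PR through C11-C20. This reply stands in part. A reader might infer that the SAP settles the matter and that unconfirmed responses do enter the confirmed rate. The documents do not support that, because it is one reading of an internal conflict. The reply does not remove the conflict, since the two readings give different BORs from the same scans.

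Second, the under-28-day case is not a departure from the protocol's footnote. That footnote has the same sentence for CR followed by PR, also without an interval, and the interval sits in Protocol 10.2.2. This stands. The departure from the protocol concerns CR followed by SD.

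Third, CR followed by SD is nearly excluded by the response definitions. It is rare, but a small target, such as a single lymph node, can produce it.

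Finally, because the lower limit moves from 14.1% to 16.2% at n = 40, a reader might infer that the footnote carries a cohort past the 15% futility reference. It does not. The futility guideline counts responders (1 or fewer of 15, 4 or fewer of 25), enrollment is complete at 40, and no rule compares a confidence limit with 15%.

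**Conclusion.** The point holds as a conflict of wording with a one-way effect. Followed literally, the footnote gives PR where rows C12, C13, C17 and C18 give SD. For CR followed by SD it also gives a result that the protocol table never allows. CR re-labelled PR and followed by PR at least 28 days later is confirmed and unaffected.

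The literal reading can only raise ORR. On the assumption of 0 or 1 affected subject per cohort, the shift is at most 2.5 points in a 40-subject cohort, 5.0 in a 20-subject cohort and 8.3 in the 12-subject cohort. ORR is a descriptive secondary endpoint, and no stated decision threshold changes. The correction is still worth making, because a BOR algorithm should return one answer for one set of scans.

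**What to change.** In SAP Appendix C:

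1. Replace the footnote's closing clause, which sets the best response to PR, with: *and BOR is then derived from rows C11-C20 using the corrected response*.
2. In C3 and C8, separate T2 = SD from T2 = PR. Limit the footnote's PR branch to T2 = PR. Give T2 = SD the protocol result: SD if the 49-day criterion is met, otherwise PD.
3. Add a row for an unconfirmed PR when both scans precede day 49, which C11-C20 lack. The sponsor must choose the outcome. Row C23 scores the parallel case of SD at T1 as NE.

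The cost is a few words, the split and added rows, and a small change to the BOR program. No new data are needed. ORR may be slightly lower in rare cases.
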